#### 8.4.8.2 Rash Events

The following rash events (Table 5) are defined as AESI in this study. Refer to the AESI guidance document (or equivalent) for the most updated list of terms, definitions, and additional details.

Table 5 Terms for Rash Events

Term	Definition		
Acute generalized exanthematous pustulosis (AGEP)	A disorder characterized by fever and sterile pustules, circumscribed and elevated skin lesions filled with pus.		
Drug eruption	An adverse skin reaction to a drug, not otherwise included in this table of rash terms.		
Drug reaction with eosinophilia and systemic symptoms (DRESS)	A disorder characterized by fever, influenza-like symptoms, skin rash, eosinophilia, with or without atypical lymphocytes, elevated transaminase concentration, and/or impaired renal function.		

Term	Definition	
Erythema multiforme	A disorder characterized by target lesions (a pink-red ring around a pale center).	
Generalized rash of exfoliative nature (including dermatitis exfoliative and exfoliative rash)	A disorder characterized by generalized inflammatory erythema and exfoliation. The inflammatory process involves >90% of the body surface area.	
Stevens-Johnson syndrome (SJS)	A disorder characterized by ≤30% total body skin area separation of dermis. The syndrome is thought to be a hypersensitivity complex affecting the skin and the mucous membranes.	
Toxic epidermal necrolysis (TEN)	A disorder characterized by >30% total body skin area separation of dermis. The syndrome is thought to be a hypersensitivity complex affecting the skin and the mucous membranes.	
Urticaria	A disorder characterized by an itchy skin eruption characterized by wheals with pale interiors and well-defined red margins.	

The investigator or medically qualified designee will receive support from the Sponsor to assist in identifying the rash AESI terms listed above (eg, representative photographic images) in addition to detailed instructions on the process from identification to photographic image submission. At Visit 1, the investigator will provide anticipatory guidance to the legally acceptable representative for suspected rash events.

If any rash event is reported in the eDiary (through Day 42) or during weekly surveillance calls, further assessment for AESI by the site may be required. The site must call the legally acceptable representative for additional information; if it is determined that an onsite assessment for AESI is required, a site visit should be conducted as soon as possible after becoming aware of the rash event or within 3 days. Photographs (see Section 8.4.8.2.1) and a dermatology consultation (see Section 8.4.8.2.2) may also be required.

In addition, the legally acceptable representative should call the site as soon as possible if they suspect a rash AESI or within 3 days of event onset.

#### 8.4.8.2.1 Photography

If a participant has a suspected or confirmed rash AESI on evaluation, photographs must be taken. For all other rashes (non-AESI), photographs are not required.

Photographs will be taken to document the visual appearance and scope of dermal involvement. Whenever possible, photographs of participant's faces or any other identifying features should be avoided or redacted. Sites should follow local policies for maintaining participant confidentiality and privacy.

Before the end of the visit, the photographs should be reviewed by site staff to ensure they meet the imaging vendor requirements; additional photographs should be taken if needed. All photographs will be uploaded to the central vendor repository.

The imaging vendor will provide the following to each site:

- Training
- Details and requirements for the photographs (eg, number of photos, lighting)
- Instructions for uploading photographs to the vendor repository
- All imaging equipment

# 8.4.8.2.2 **Dermatology Consultation**

Severe rash AESI (Grade 3 and Grade 4) are unusual in general pediatric practice and therefore require evaluation by dermatologic specialists.

If the investigator determines that the suspected rash is indeed a Grade 3 or 4 AESI, every effort should be made to schedule a consultation with a local dermatologist (pediatric dermatologist is preferred where possible). This consultation with the local dermatologist should occur as soon as possible or within 3 days from the time the site diagnoses the Grade 3 or Grade 4 AESI.

The purpose of the dermatology consultation is to gain confirmation of the rash diagnosis. This consultation should be conducted per local standards of care. The dermatologist should be provided access to the photos taken at the site visit and copies of relevant source documents collected for the purpose of this study.

After the dermatology consultation, the local dermatologist's assessment and recommendations should be obtained. The diagnosis from the local dermatologist as well as any procedures or other intervention should be recorded on the appropriate eCRFs and added to the source documents.

See the AESI guidance document (or equivalent) for additional details.

### 8.5 Treatment of Overdose

In this study, an overdose is any dose higher than the protocol-defined dose.

No specific information is available on the treatment of overdose.

#### 8.6 Pharmacokinetics

The decision as to which serum samples collected will be tested to evaluate PK will be determined by the Sponsor. If indicated, these samples may also be tested and/or pooled for testing in an exploratory manner for metabolites and/or additional markers.

Confidential

See the Pharmacokinetics/Immunogenicity/Pharmacodynamics schedule in the SoA for the timing of each blood draw. Detailed instructions including blood volumes to be drawn are provided in the laboratory manual.

# 8.7 Immunogenicity

### 8.7.1 Blood Collection for Antidrug Antibodies (ADA) Assay

Sample collection, storage, and shipment instructions for serum samples are provided in the laboratory manual.

See the Pharmacokinetics/Immunogenicity/Pharmacodynamics schedule in the SoA for the timing of each blood draw.

## 8.8 Pharmacodynamics

# 8.8.1 Blood Collection for Serum Neutralizing Antibodies Against RSV (SNA) Assav

Sample collection, storage, and shipment instructions for pharmacodynamic samples are provided in the laboratory manual.

See the Pharmacokinetics/Immunogenicity/Pharmacodynamics schedule in the SoA for the timing of each blood draw.

# 8.9 Gene Sequencing and Sensitivity Testing

# 8.9.1 Nasopharyngeal Sample Collection for RT-PCR Testing and RSV F Gene Sequencing for Sensitivity to MK-1654

See the SoA (Section 1.3) and Section 8.2.3 for the timing of collection of the NP sample for RT-PCR testing for respiratory pathogen identification.

RSV F gene sequencing will only be performed if the NP specimen tests positive for RSV.

Detailed instructions are provided in the laboratory manual.

#### 8.10 Biomarkers

Biomarkers are not evaluated in this study.

# 8.11 Future Biomedical Research Sample Collection

If the participant's legally acceptable representative provides documented informed consent for future biomedical research, the following specimens will be obtained as part of future biomedical research:

DNA for future research

• Leftover serum from the PK assay will be stored for future research.

- Leftover serum from the ADA, SNA, and additional ADA characterization assays will be stored for future research.
- Leftover NP swabs from RT-PCR testing will be stored for future research.

#### 8.12 Medical Resource Utilization and Health Economics

Medical Resource Utilization and Health Economics are not evaluated in this study.

#### 8.13 Visit Requirements

Visit requirements are outlined in Section 1.3. Specific procedure-related details are provided in Section 8.1 through Section 8.11. Additional specific requirements are detailed below.

# 8.13.1 Screening (Visit 1 Predose)

At Visit 1, potential participants will be evaluated to determine whether they meet entry requirements as set forth in Section 5. Potential participants will be screened at the study site.

Infants with a recent illness with fever (rectal temperature  $\geq 100.5^{\circ}F$  [ $\geq 38.1^{\circ}C$ ] or axillary temperature  $\geq 100.0^{\circ}F$  [ $\geq 37.8^{\circ}C$ ]) within 72 hours predose at Visit 1 before administration of study intervention are not eligible, but may be rescreened (see Section 5.2 Exclusion Criterion 4).

Participants may be rescreened up to 4 times. Screening procedures listed in the SoA (including consent review; see Section 1.3.1) should be repeated at each rescreen visit.

#### 8.13.1.1 Predose Nasopharyngeal Sample Collection for RT-PCR Testing

If symptoms of respiratory infection have been present within 7 days before Visit 1, an NP sample should be collected. Collecting an NP sample at Visit 1 does not exclude an infant from participating in the study.

#### 8.13.2 Randomization/Dose Administration/Observation (Visit 1)

If a participant is deemed eligible for the study, and completes all other predose procedures, the participant will be assigned a unique treatment/randomization number by the IRT system.

All participants will also be randomized by IRT to 1 of the 2 different blood sampling groups (Group 1 or Group 2) that differ in the schedule of serum PK, ADA, and SNA sampling (see Section 1.3.1). Participants will then be assigned by IRT to 1 of the 2 subgroups (a or b) that differ in the tests to be performed.

Predose samples should be collected from randomized participants only. Samples should be collected after randomization in the IRT system but before dose administration. If the predose blood sample cannot be collected after 3 attempts, the dose should be administered.

After randomization in the IRT system, participants will receive study intervention administered as a single IM injection at the study site as described in Section 6.1 and Section 8.

Participants will be observed at the study site for at least 30 minutes postdose for any immediate AEs (see Section 8.3.4). This observation must be performed by the blinded investigator and/or study staff.

Vital sign measurements should be repeated at the end of the 30-minute postdose safety observation period.

# 8.13.3 Delay in Randomization and Study Medication Administration

All efforts should be made to randomize participants and administer study medication on Day 1 after predose screening procedures as per protocol. However, if randomization and study medication administration cannot be conducted on the same day as screening, they may be conducted within 5 days of the predose screening procedures.

Prior to randomization in the IRT system and administration of study medication (Day 1), the site should confirm participant's eligibility by repeating vital signs measurements, the full physical examination (including weight), and review the eligibility criteria and the informed consent.

### 8.13.4 Early Withdrawal Visit

If the legally acceptable representative withdraws consent prior to the last study visit, the participant should be brought in for a final visit (at the study site, at home, or at an alternate study site location; see Section 8.13.5) as follows:

- First 1650 participants: Complete all assessments and procedures indicated for Visit 8 in the SoA (Section 1.3.2).
- Remaining participants: Complete all assessments and procedures indicated for Visit 7 in the SoA (Section 1.3.1).

If the participant withdraws consent while attending a scheduled visit, any additional assessments and procedures needed for the final study visit should be conducted in addition to the assessments and procedures for the scheduled visit.

# 8.13.5 Visits at the Study Site, at Home, or at an Alternate Study Site Location

Every attempt should be made to assess the participant at the study site for all scheduled study visits (see Section 1.3.1 and Section 1.3.2) and for any unscheduled visit to assess possible respiratory infection symptoms or a suspected AESI (see Section 8.2.2 and Section 8.4.8). However, if this is not possible, additional efforts should be made to ensure the per-protocol assessments are conducted for these visits.

A visit at the study site is required at Visit 1 (Day 1). Study site visits are preferred for Visits 2 through 8 to ensure the participants are seen in person by the investigator and site staff in the event respiratory infection symptoms or a suspected AESI are present. See Section 1.3.1 and Section 1.3.2 for the visit schedules.

If circumstances do not support a visit at the study site, a home visit by the site personnel or a healthcare service provider (eg, home healthcare vendor) or a visit to an alternate study site location may be appropriate to perform study assessments and procedures per the SoA, where available and when permitted by local regulations and IRB/IEC. All indicated study procedures should be completed, including blood draws. The documentation from the visit should be provided to the investigator or medically qualified designee (consistent with local requirements) for review and assessment per institutional standard. Also, this documentation should be provided to site staff for data entry purposes.

Refer to the home visit manual (or equivalent) for details.

#### 9 STATISTICAL ANALYSIS PLAN

This section outlines the statistical analysis strategy and procedures for the study. If, after the study has begun, but prior to any unblinding/final database lock, changes are made to primary and/or key secondary hypotheses, or the statistical methods related to those hypotheses, then the protocol will be amended (consistent with ICH Guideline E-9). Changes to tertiary or other nonconfirmatory analyses made after the protocol has been finalized, but prior to unblinding/final database lock, will be documented in an sSAP and referenced in the CSR for the study. Post hoc tertiary analyses will be clearly identified in the CSR.

# 9.1 Statistical Analysis Plan Summary

Key elements of the statistical analysis plan are summarized below; the comprehensive plan is provided in Section 9.2 through Section 9.12.

Study Design Overview	A Phase 2b/3 Double-Blind, Randomized, Placebo-Controlled Study to Evaluate the Efficacy and Safety of MK-1654 in Healthy Pre-Term and Full-Term Infants
Treatment Assignment	Participants will be assigned randomly in a 2:1 ratio to receive a single dose of MK-1654 or placebo. Randomization will be stratified by region (Southern Hemisphere and Northern Hemisphere), gestational age (≥29 to <35 weeks; ≥35 weeks), and chronological age at the time of consent (<6 months; ≥6 months).
Analysis Populations	Efficacy: Full Analysis Set (FAS) Safety: All Participants as Treated (APaT)

Primary Endpoint(s)	
 
Efficacy: Number of participants with RSV-MALRI in the MK-1654 and placebo groups from Days 1 through 150 postdose.
 
Safety: Number of participants experiencing solicited injection-site AEs from Days 1 through 5 postdose, solicited daily body temperature to identify fever from Days 1 through 5 postdose, solicited systemic AEs from Days 1 through 5 postdose, anaphylaxis/hypersensitivity AESI from Days 1 through 42 postdose, rash AESI from Days 1 through 42 postdose, nonserious AEs from Days 1 through 42 postdose, and SAEs through the duration of study participation.
 
	
Key Secondary Endpoints	
 
Efficacy: Number of participants with RSV hospitalization in the MK-1654 and placebo groups from Days 1 through 150 postdose.
 
Efficacy: Number of participants with RSV-MALRI in the MK-1654 and placebo groups from Days 1 through 180 postdose.
 
	
Statistical Methods for Key Efficacy Analyses	The primary efficacy hypothesis will be evaluated by calculating the efficacy of MK-1654 compared to placebo with respect to the RSV-MALRI endpoint. The p-value for testing the primary hypothesis that efficacy>25% as well as estimation of the 95% CI of efficacy will be based on the modified Poisson regression with robust variance proposed by Zou [Zou, G. 2004].	
Statistical Methods for Key Safety Analyses	There are no a priori clinical events identified in this trial as Tier 1 events. Tier 2 events identified in this trial include solicited injection-site AEs; solicited daily body temperature to identify fever; solicited systemic AEs; drug-related AEs; any serious AEs; discontinuations due to AEs; anaphylaxis/hypersensitivity AESI; rash AESI; nonserious AEs; and AEs by system organ class observed in ≥1% of participants in at least one group. Estimates of 95% CIs for between-treatment differences in the percentage of participants with events will be calculated using the Miettinen and Nurminen method [Miettinen, O. and Nurminen, M. 1985].	
Interim Analyses	Two IAs are planned in this study. The first IA (IA#1) will be conducted after the last participant in the Phase 2b cohort completes the Day 42 visit. Summaries of the safety, available PK, and efficacy for the endpoints of RSV-associated MALRI and hospitalization will be assessed at the IA#1 to evaluate the benefit versus risk for continued enrollment. The second IA (IA#2) will be conducted when 40 total cases of RSV-associated MALRI have accrued across the MK-1654 and placebo groups. Futility of the primary hypothesis will be assessed at IA#2. The IAs will be performed by an unblinded statistician and results will be reviewed by an eDMC. Details are provided in Section 9.7.	
Multiplicity	The overall 1-sided Type 1 error in testing the efficacy hypotheses is controlled at 2.5% based on gatekeeping procedure. The primary efficacy hypothesis will be tested at an overall 1-sided Type 1 error of 2.5%, as discussed in Section 9.9.1.1. The secondary efficacy hypothesis regarding RSV hospitalization from Days 1 through 150 postdose will be tested at 1-sided Type 1 error of 2.5% only if the primary efficacy hypothesis is successfully demonstrated, as discussed in Section 9.9.1.2.	

**C** Confidential

Sample Size and Power	This study will randomize approximately 3300 healthy infants in a 2:1 allocation ratio into the MK-1654 group and the placebo group. Approximately 167 total cases of RSV-MALRI in the MK-1654 and placebo groups are expected to accrue by the end of the study. For RSV-MALRI, the study has >95% power to demonstrate that the efficacy of MK-1654 compared to placebo to prevent RSV-MALRI is >25% if the underlying efficacy is 70% at an overall 1-sided Type 1 error of 2.5%. A total of approximately 33 cases of RSV hospitalization in the MK-1654 and placebo groups are expected to accrue by the end of the study. For RSV hospitalization, the study has 93.6% power to demonstrate that the efficacy of MK-1654 compared to placebo to prevent RSV
	hospitalization is >0% if the underlying efficacy is 70% at an overall 1-sided Type 1 error of 2.5%.

# 9.2 Responsibility for Analyses/In-house Blinding

The statistical analysis of the data obtained from this study will be the responsibility of the Clinical Biostatistics department of the Sponsor.

This study will be conducted as a double-blind study under in-house blinding procedures. The official, final database will not be unblinded until medical/scientific review has been performed, protocol deviations have been identified, and data have been declared final and complete.

The Clinical Biostatistics department will generate the randomized allocation schedule(s) for study treatment assignment. Randomization will be implemented using IRT.

Blinding issues related to the planned IAs are described in Section 9.7.

## 9.3 Hypotheses/Estimation

Objectives and hypotheses of the study are stated in Section 3.

#### 9.4 Analysis Endpoints

The efficacy, PK, pharmacodynamics, immunogenicity, and safety endpoints that will be evaluated are listed below.

## 9.4.1 Efficacy/Pharmacokinetics/Pharmacodynamics/Immunogenicity Endpoints

# **Efficacy Endpoints**

The primary efficacy endpoint that will be used to evaluate and test the primary efficacy hypothesis is the number of participants with RSV-associated outpatient and inpatient MALRI occurring from Days 1 through 150 postdose, as described in Section 4.2.1.1. RSV-associated outpatient and inpatient MALRI is defined by the presence of the following seen in an outpatient or inpatient clinical setting: cough or difficulty breathing; AND 1 or more of the following: wheezing, chest wall in-drawing/retractions, rales/crackles, hypoxemia,

PROTOCOL/AMENDMENT NO.: 004-05

tachypnea, dehydration due to respiratory symptoms; AND RSV-positive RT-PCR NP sample. The secondary efficacy endpoints are:

- Number of participants with RSV-associated hospitalization from Days 1 through 150 postdose, defined as hospital admission for respiratory illness; AND RSV-positive RT-PCR NP sample
- Number of participants with RSV-associated outpatient and inpatient MALRI from Days 1 through 180 postdose

The following are the tertiary efficacy endpoints for this study:

- Number of participants with RSV-associated outpatient and inpatient severe MALRI from Days 1 through 150 postdose
- Number of participants with RSV-associated outpatient and inpatient severe MALRI from Days 1 through 180 postdose
- Number of participants with RSV-associated hospitalization from Days 1 through 180 postdose
- Number of participants with outpatient and inpatient MALRI due to any cause from Days 1 through 150 postdose
- Number of participants with RSV-associated outpatient and inpatient MALRI from Days 365 through 515 postdose
- Number of participants with RSV-associated hospitalization from Days 365 through 515 postdose
- Number of participants hospitalized with RSV-associated LRI from Days 1 through 150 postdose
- Number of participants hospitalized with RSV-associated LRI from Days 1 through 180 postdose
- Number of participants hospitalized with LRI due to any cause from Days 1 through 150 postdose
- Number of participants with non-RSV-associated outpatient and inpatient MALRI from Days 1 through 150 postdose
- Number of participants with RSV-associated outpatient and inpatient MALRI excluding cases where other pathogens are found from Days 1 through 150 postdose
- Number of participants with RSV-associated outpatient and inpatient ARI from Days 1 through 150 postdose

- Number of participants with RSV-associated outpatient and inpatient ARI from Days 1 through 180 postdose
- Number of participants with physician-assessed wheezing from Days 1 through 180 postdose
- Number of participants with physician-assessed wheezing from Days 365 through 515 postdose

# **Pharmacokinetics Endpoints**

The tertiary PK endpoints are the serum PK concentration of MK-1654 at Days 7, 150, and 240 postdose.

#### Pharmacodynamics Endpoints

The tertiary pharmacodynamics endpoints are SNA titers against RSV A at Day 1 (predose) and Days 7, 150, 240, 365, and 515 postdose.

# Immunogenicity Endpoints

The tertiary immunogenicity endpoints are ADA to MK-1654 at Day 1 (predose) and Days 150, 240, 365, and 515 postdose.

# **Additional Tertiary Endpoints**

The additional tertiary endpoint is RSV F gene sequence determined by deep sequencing in NP samples from infants infected with RSV.

# 9.4.2 Safety Endpoints

Safety and tolerability of MK-1654 in this study will be assessed by clinical review of all relevant parameters including AEs and laboratory values. The endpoints that will be used to assess the safety and tolerability of MK-1654 include the following:

- Number of participants experiencing solicited injection-site AEs (redness/erythema, swelling, and pain/tenderness) from Days 1 through 5 postdose
- Number of participants experiencing solicited daily body temperature, with fever defined as rectal temperature ≥102.2°F (≥39.0°C) or axillary temperature ≥101.7°F (≥38.7°C), from Days 1 through 5 postdose
- Number of participants experiencing solicited systemic AEs (irritability, drowsiness, and appetite lost) from Days 1 through 5 postdose
- Number of participants with anaphylaxis/hypersensitivity AESI from Days 1 through 42 postdose

- Number of participants with rash AESI from Days 1 through 42 postdose
- Number of participants experiencing nonserious AEs occurring from Days 1 through 42 postdose
- Number of participants experiencing SAEs through the duration of study participation (from the time the consent form is signed through completion of the participant's participation in the study; for complete details on SAE data collection, see Section 10.3.5).

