# 8.4.6 Disease-related Events and/or Disease-related Outcomes Not Qualifying as AEs or SAEs

Not applicable for this study.

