# 9.6.2 Statistical Methods for Safety Analyses

Safety and tolerability will be assessed by clinical review of all relevant parameters including AEs. All safety summaries will be provided separately for the first and second RSV seasons.

The analysis of safety results will follow a tiered approach (Table 7). AEs (specific terms as well as system organ class terms) and events that meet predefined limits of change (PDLCs) in laboratory and vital signs parameters are either pre-specified as "Tier 1" endpoints or will be classified as belonging to "Tier 2" or "Tier 3" based on the observed proportions of participants with an event.

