#### **Tier 1 Events**

Safety parameters or AESI that are identified a priori constitute "Tier 1" safety endpoints that will be subject to inferential testing for statistical significance. There are no Tier 1 events for this protocol as no treatment-related SAEs have been observed in the Phase 1 studies of MK-1654.

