#### **Tier 2 Events**

Membership in Tier 2 requires that at least 1% participants in any treatment group exhibit the event; OR AEs listed in Table 7. All other AEs will belong to Tier 3. Maximum body temperature will be summarized using Brighton Collaboration cutoffs.

The threshold of at least 1% was chosen to draw clinical meaningful inference. When less than 1% of participants report AEs in both groups, the 95% CI for the between-group difference may exclude zero. However, the clinical significance of these differences is unknown given the small number of participants who report AEs. Because many 95% CIs for Tier 2 events may be provided without adjustment for multiplicity, the CIs should be regarded as a helpful descriptive measure to be used in review, not a formal method for assessing the statistical significance of the between-group differences in AEs.

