### **Tier 3 Events**

Safety endpoints that are not Tier 1 or 2 events are considered Tier 3 events. Only point estimates by treatment group are provided for Tier 3 safety parameters.

Table 7 Analysis Strategy for Safety Parameters

Safety Tier	Safety Endpoint	95% CI for Comparison of MK-1654 and Placebo	Descriptive Statistics
Tier 2	Any AE a	X	X
	Any Serious AE	X	X
	Any Drug-related AE	X	X
	Any Serious and Drug-related AE	X	X
	Discontinuation due to AE	X	X
	Solicited Injection-site AEs Days 1-5 Postdose	X	X
	Solicited Daily Body Temperature Days 1-5 Postdose	Х	X
	Solicited Systemic AEs Days 1-5 Postdose	X	X
	Anaphylaxis/hypersensitivity AESI Days 1-42 Postdose	Х	X
	Rash AESI Days 1-42 Postdose	X	X
	Nonserious AEs Days 1-42 Postdose	X	X
	AEs by SOC (incidence ≥1% of participants in 1 of the treatment groups)	Х	X
Tier 3	AEs by SOC (incidence <1% of participants in all of the treatment groups)		X

AE=adverse event; AESI=adverse event(s) of special interest; SAE=serious adverse event; CI=confidence interval; SOC=System Organ Class; X=results will be provided.

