### c. Requires inpatient hospitalization or prolongation of existing hospitalization

Hospitalization is defined as an inpatient admission, regardless of length of stay, even
if the hospitalization is a precautionary measure for continued observation. (Note:
Hospitalization for an elective procedure to treat a pre-existing condition that has not
worsened is not an SAE.) A pre-existing condition is a clinical condition that is
diagnosed prior to the use of an MSD product and is documented in the participant's
medical history.

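### RSV admissions count both as an efficacy endpoint and as SAEs, and no planned row shows the SAE difference net of them

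*Combined protocol and SAP*

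**What the plan says.** SAEs are part of the primary safety objective (Section 3), and Section 9.4.2 counts the "Number of participants experiencing SAEs through the duration of study participation". Section 10.3.3(c) makes an event serious if it "Requires inpatient hospitalization or prolongation of existing hospitalization", whatever the length of stay. Section 8.4.6, where disease-related events could be kept out of AE and SAE reporting, reads "Not applicable for this study". Section 9.4.1 lists RSV-associated hospitalization through Day 150 as a secondary efficacy endpoint.

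Table 7 compares any serious AE between groups with a 95% CI. The closest narrower row is "Any Serious and Drug-related AE". Section 9.6.2 also places "AEs (specific terms as well as system organ class terms") in tiers. Apart from the events listed in Table 7, Tier 2 requires that "at least 1% participants in any treatment group exhibit the event". The one stated split of the safety displays is by season: "All safety summaries will be provided separately for the first and second RSV seasons". None of this is formal testing: "There are no Tier 1 events for this protocol", and the Tier 2 intervals are declared descriptive.

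**The concern.** The same admission is scored twice, once as efficacy and once as safety. If MK-1654 prevents RSV admissions, the all-SAE rate on MK-1654 falls for that reason alone. An excess of non-RSV SAEs of similar size would then be offset in the main SAE comparison, and a larger one would be diluted. The reverse also applies: a lower SAE rate on MK-1654 could be read as evidence of tolerability when it only restates efficacy. What is at stake is how a primary safety endpoint is read.

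**Working it through.** **Inputs from the plan (Sections 9.9.1.2 and 9.9.2).** RSV hospitalization 2.0% on placebo and 0.6% on MK-1654 per season (efficacy 70%); attrition 5%; 1100 placebo and 2200 MK-1654 infants.

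**Input assumed.** The non-RSV SAE rate *b*. The documents give none, so 2% to 20% is shown, taken as independent of RSV admission.

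**Plan's own figure.** 0.95 × (1100 × 0.02 + 2200 × 0.006) = 20.9 + 12.5 = 33.4 admissions, against about 33 stated. It reproduces.

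**Shift from efficacy alone, no non-RSV difference.**
- No attrition, no overlap: 0.6 - 2.0 = -1.40 points.
- With attrition: 0.95 × (-1.40) = -1.33 points.
- With attrition and overlap: -1.33 × (1 - *b*).

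| *b* (assumed) | Shift, points |
|---|---|
| 2% | -1.30 |
| 5% | -1.26 |
| 10% | -1.20 |
| 15% | -1.13 |
| 20% | -1.06 |

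The size depends on efficacy. At *b* = 5% with attrition it is 0.95 × (-1.00) × 0.95 = -0.90 if efficacy is 50%, and 0.95 × (-1.80) × 0.95 = -1.62 if it is 90%.

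**Scale.** Table 9 gives 2.0% against 3.8% as a detectable pair, 1.8 points apart. Taken as non-RSV SAE rates, with RSV admissions added (no attrition), they become 2.0 + 2.0 - 0.04 = 3.96% and 3.8 + 0.6 - 0.02 = 4.38%. The displayed difference is 0.42 points.

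**What a net row would add.** With attrition, RSV admission rates are 1.90% and 0.57%. The non-RSV excess *e* that is exactly cancelled solves (1 - *b* - *e*)(1 - 0.0057) = (1 - *b*)(1 - 0.019), so *e* = 1.33% × (1 - *b*)/0.9943. Miettinen-Nurminen 95% CIs at the expected counts, in points:

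| *b* | Net of RSV | All SAEs |
|---|---|---|
| 2% | +1.31 (0.11 to 2.40) | 0.00 (-1.49 to 1.33) |
| 2.5% | +1.30 (0.00 to 2.49) | 0.00 (-1.57 to 1.42) |
| 3% | +1.30 (-0.11 to 2.57) | 0.00 (-1.65 to 1.49) |
| 5% | +1.27 (-0.45 to 2.86) | 0.00 (-1.91 to 1.76) |
| 10% | +1.20 (-1.08 to 3.36) | 0.00 (-2.40 to 2.27) |

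So the net interval for a fully cancelled excess excludes 0 only below a background of about 2.5%. Above that the row corrects the estimate, but its interval still includes 0.

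With no non-RSV difference and *b* = 2%, the all-SAE row would show -1.30 (-2.74 to -0.07). That is true for all causes but says nothing about non-RSV safety.

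**Do existing displays fill the gap?**
- The serious and drug-related row rests on the investigator's causality assessment, so it also drops every other SAE considered unrelated.
- Rows by SOC or term follow the recorded diagnosis (Section 10.3.5), not the PCR result. They are not limited to SAEs, because all AEs are collected to Day 42, and they give no participant total.
- Subtracting the efficacy counts gets near the point estimate but gives no CI. Efficacy is analysed as randomized with a central PCR result (Section 9.5.1) and safety as treated (Section 9.5.4), and one infant can have both kinds of event.

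**The case against.** The strongest reply is that the plan contains no error. The all-SAE row is a correct all-cause comparison, no test depends on it, and the documents give no sign of a non-RSV excess. All of that stands. A reader might infer that the SAE analysis is biased or that it conceals a harm; the documents support neither.

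The plan also has safeguards. The eDMC reviews safety together with RSV incidence at least every six months during enrollment (Section 9.7). Section 9.4.1 plans any-cause LRI hospitalization, hospitalization with RSV-associated LRI, and non-RSV MALRI by group. These help to locate an imbalance, particularly a respiratory one. None yields a net count of participants with SAEs or an interval for it, so the gap is narrowed but not closed.

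A net row has its own weakness: it conditions on a post-dose PCR result. If MK-1654 lowers RSV positivity, infants admitted for another cause with incidental RSV would be removed more often from placebo, which can tilt the row against MK-1654. This stands too. It is a reason to make the row supportive and to state the limitation, not a reason to omit it.

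**Conclusion.** The point holds as a cheap improvement to the reading of a primary safety endpoint, not as a fault in the planned comparison. The plan's rates give a shift of -1.40 points, or -1.33 with attrition. Everything smaller rests on an assumed non-RSV SAE rate and independent overlap.

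Three stronger readings go too far:
- A range reaching down to about -1.1 is not the plan's own. It needs an assumed background of about 17% with attrition (1 - 1.1/1.33) or 21% without (1 - 1.1/1.4).
- The shift is not established for the whole study. The rates are per season for a Days 1-150 endpoint, while SAEs run to Day 365 or Day 515.
- A net row would not generally reveal a cancelled excess. Its interval excludes 0 only below a background of about 2.5%; elsewhere the gain is a corrected estimate.

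**What to change.** Keep the any-serious-AE row. Before unblinding, add a supportive row to Table 7, or to the sSAP as a nonconfirmatory change under Section 9:
- **Definition:** participants with at least one SAE other than a hospital admission for respiratory illness with an RSV-positive central-laboratory PCR, sampled within the Section 9.5.1 window. Give the between-group difference and 95% CI.
- **Exclude events, not participants,** so that an infant who also has another SAE still counts.
- **Sensitivity version:** include local PCR results, as Section 9.5.1 does for efficacy.
- **Timing:** report it within the planned season summaries. A Days 1-180 display, covering the first period of active surveillance, is optional.
- **Stated limits:** RSV admissions without a PCR result stay in the count, and incidental RSV-positive admissions may be removed more often from placebo. The row is therefore read beside the all-SAE row.

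The cost is SAP or sSAP wording and a little extra output. Central PCR results and available local ones are already collected (Section 8.2.3). The date matters because the sponsor team is unblinded at the Day 180 database lock while SAE follow-up continues (Section 9.7), and a row defined after that could be called post hoc.
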